### 7.3.2.4 Escape analysis

Only patient who attained UFC normalization during the study will be included in this analysis, where escape is defined as the loss of UFC control (i.e. UFC  $>$  ULN) on at least 2 consecutive visits at the highest tolerated dose after previously attaining UFC normalization. "First-time escape" is used to describe the first occurrence of 2 consecutive visits with uncontrolled UFC at the patient's highest tolerated dose after attaining UFC normalization. Time to escape is defined as the number of weeks from the visit of first UFC normalization (mUFC  $\leq 1 \times$  ULN) to the first visit of first-time escape. The definition for "highest tolerable dose" of LCI699 is provided in this paragraph. For patients who have no safety issue, 30 mg bid is the highest

tolerated dose. For patients who have dose reduction(s) because of an intolerable adverse event, the highest tolerated dose is the highest dose at which no AE requiring dose reduction is reported. For patients who discontinue the study due to AE, the highest tolerated dose is the highest prior dose at which no intolerable AE was reported. For all other situations (i.e., LCI699 dose is < 30mg bid, and there has been no AE leading to dose reduction or study drug discontinuation reported at the effective treatment dose), patients will be considered as not reaching their highest tolerated dose.

The median time to escape and corresponding two-sided 95% confidence interval will be calculated using Kaplan-Meier methodology for each cohort. The Kaplan-Meier curves will be presented. In this analysis, a patient who never had two consecutive visits with uncontrolled UFC at his/her highest tolerated dose will be censored at his/her last visit with mUFC assessment. In addition, time to escape will be summarized using descriptive statistics by cohort for patients who meet escape criteria.

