One of the secondary objectives is to assess escape (Section 2.2). The definition of escape has been modified to include its relation to the highest tolerated dose of LCI699. The concept of escape refers to loss of control of UFC after having attained normalization of UFC on LCI699 therapy at an earlier time point. In this study, it is permitted to increase the dose of LCI699 not only during the dose titration phase (weeks 1-10), but also during the treatment period (weeks 11-22) of the core study, and during the extension study if applicable. This is intended to mimic clinical practice. The additional requirement to have uncontrolled UFC at the highest tolerated dose of LCI699 is also intended to reflect anticipated clinical use of the drug. The highest tolerated dose is the highest dose without a drug-suspected adverse event (AE), up to the maximum LCI699 dose of 30mg bid.

The requirement of uncontrolled UFC on two consecutive visits is intended to ensure that the elevated UFC is not due to lab error or variations just above the upper limit of the normal reference range. Escape events will be described by a Kaplan-Meier analysis of “time to escape,” i.e., the time (in weeks) from the first normalization of UFC to the first of two consecutive uncontrolled UFC levels (Section 9.5.2).

Changes to the protocol

Changes to specific sections of the protocol are shown in the track changes version of the protocol using ~~strike through red font for deletions~~ and red underlined for insertions.

Protocol synopsis: Edited to be consistent with changes throughout the protocol.

Assessment Schedules: Table has been updated to reflect the intensive cardiac monitoring (ECG and Holter) and the additional interim visits when dose escalation should occur if needed.

[figure not shown]
Section 1.1.1.1 (Table 1-1): Safety margin multiples for the 30 mg bid dose have been added to Table 1-1.

Section 1.1.1.4: This section has been updated to include estimation of PK exposure at 30 mg bid, and added background on emerging preclinical data regarding LCI699 metabolism.

Section 2.2: Secondary objective on escape, and the definition of escape, were modified.

Section 3.1: Addition of the interim dose escalation visits and update of Figure 3-1 to reflect new design with interim visits. Section updated (including Figure 3-1) to reflect the change of the maximum dose strength of 30 mg.

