There were no study drug related discontinuations, deaths or serious AEs of suspected drug relationship.

The dose at which patients had a normalization of UFC varied. Overall, all 11 patients had at least one UFC <ULN in recorded visits. One patient had normal UFC with a dose of 2 mg bid, 3 patients had normal UFC with a dose of 5 mg bid, 3 patients had normal UFC with a dose of 10 mg bid, one patient had normal UFC with a dose of 15 mg bid, two patients had normal UFC with a dose of 20 mg bid and one patient had a normal UFC with a dose of 50 mg bid.

LCI699 was generally well tolerated. There were no discontinuations due to adverse events or serious AEs of suspected drug relationship reported. Eleven patients reported at least one AE. Four patients experienced AEs consistent with cortisol withdrawal and they all improved upon dose reduction.

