9.5.2 Escape analysis

Only patients who attained UFC normalization during the study will be included in the escape analysis, where escape is defined as the loss of UFC control (i.e. UFC > ULN) on at least 2 consecutive visits at the highest tolerated dose after previously attaining UFC normalization. “First-time escape” is used to describe the first occurrence of 2 consecutive visits with uncontrolled UFC at the patient’s highest tolerated dose after attaining UFC normalization. Time to escape is defined as the number of weeks from the visit of first UFC normalization (mUFC \leq 1x ULN) to the first visit of first-time escape. For patients who have no safety issue, 30 mg bid is the highest tolerated dose. For patients who have dose reduction due to safety reasons, the resulting reduced dose will be the highest tolerated dose. For patients who discontinue the study due to AEs, the dosage at discontinuation will be considered the highest tolerated dose. For all other situations, patients will be considered as not reaching their highest tolerated dose.

The median time to escape and corresponding 95% confidence interval will be calculated using Kaplan-Meier methodology for each cohort. The Kaplan-Meier curves will be presented. In this analysis, a patient who never had two consecutive visits with uncontrolled UFC at his/her highest tolerated dose will be censored at his/her last visit with mUFC assessment.

In addition, time to escape will be summarized using descriptive statistics by cohort for patients who meet escape criteria.

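### In the escape analysis one unconfirmed visit at or below ULN counts as normalization, so a patient stable just above ULN at the highest tolerated dose can be scored as escaped with no loss of drug effect

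*SAP*

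**What the plan says.** **Entry.** Protocol 9.5.2: "Only patients who attained UFC normalization during the study will be included in the escape analysis". SAP 7.3.2.4 repeats this, and both documents define normalization as mUFC at or below 1 x ULN. Neither asks for a confirming visit, a minimum duration of control or a particular dose at normalization.

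**Clock.** SAP 7.3.2.4: "Time to escape is defined as the number of weeks from the visit of first UFC normalization", running to the first visit of the first escape.

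**Event.** UFC above ULN on at least two "consecutive visits at the highest tolerated dose after previously attaining UFC normalization". The limit is the same ULN, with no margin.

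**Dose condition.** Protocol 9.5.2: "For patients who have no safety issue, 30 mg bid is the highest tolerated dose". Patients below 30 mg bid with no AE leading to dose reduction or discontinuation fall under the SAP's residual clause: "patients will be considered as not reaching their highest tolerated dose". They cannot have an event and are censored at their last mUFC visit.

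**Reason for two visits.** The Amendment 5 rationale in the protocol (Modified definition of escape) states: "The requirement of uncontrolled UFC on two consecutive visits is intended to ensure that the elevated UFC is not due to lab error". It adds variation just above the upper limit as a second reason. No equivalent safeguard is given for normalization.

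**The concern.** Escape is meant to capture loss of an effect that was once achieved. For a patient whose true UFC sits a little above ULN, two consecutive high visits are the expected state. The chance event is the single low visit, and that visit both admits the patient and starts the clock. Regression to the mean then supplies the escape. Confirming the high side gives little protection against this.

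Two outputs are affected: the number of escapes, and time to escape, because a chance low visit tends to be followed at once by high ones. The protocol (Sections 1.2 and 3.2) names sustainability of the cortisol reduction as a question for the study, and SAP 3.2 carries escape into the Final CSR. The Amendment 6 text reports 19 patients enrolled under Amendment 4 and 16 in extension-1. The Kaplan-Meier curves are drawn per cohort, so one or two misclassified patients would be visible in them.

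**Working it through.** The plan states no escape rate, so there is no figure to reproduce. The check asks how often a patient with no change in true UFC would be scored as escaped.

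**Inputs from the documents.** Three urines per core visit and two per extension visit (SAP 8.4). UFC visits on Days 70, 98, 126 and 154 (core), then Days 182, 210, 238, 266, 294, 322, 406 and 490 (extension-1), 12 in all.

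**Assumptions.** Protocol 3.2 acknowledges within-patient variability of UFC but gives no figure, so the CV of one 24-hour UFC is set at 20–50%. Values are lognormal and independent, true UFC is constant at c x ULN, and the patient is at the highest tolerated dose from Day 70.

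**Step 1. Chance p that a visit mean exceeds ULN (3 urines / 2 urines), by simulation.**

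| c | CV 20% | CV 30% | CV 40% | CV 50% |
|---|---|---|---|---|
| 1.1 | 0.780 / 0.728 | 0.680 / 0.637 | 0.619 / 0.580 | 0.577 / 0.542 |
| 1.3 | 0.987 / 0.964 | 0.925 / 0.874 | 0.851 / 0.791 | 0.785 / 0.724 |

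**Step 2. Four core visits.** Write q = 1 − p, L for a visit at or below ULN and H for one above. As written, escape occurs in the sequences LHH (any fourth visit), LLHH and HLHH:

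P = qp² + q²p² + qp³ = qp²(1 + q + p) = 2qp²

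- c = 1.1, CV 20%: 2 × 0.220 × 0.780² = 26.8%. CV 30%: 2 × 0.320 × 0.680² = 29.6%. CV 50%: 2 × 0.423 × 0.577² = 28.2%.
- c = 1.3, CV 20%: 2 × 0.013 × 0.987² = 2.5%. CV 50%: 2 × 0.215 × 0.785² = 26.5%.

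The maximum over all p is at p = 2/3, giving 8/27 = 29.6%. No choice of CV can push the four-visit figure above 30%.

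If normalization needs two consecutive low visits, only LLHH qualifies and P = q²p²:

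- c = 1.1: 0.220² × 0.780² = 2.9% to 0.423² × 0.577² = 6.0%.
- c = 1.3: about 0% to 0.215² × 0.785² = 2.8%.

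**Step 3. Twelve visits.** Let N be the probability of not yet being normalized, S0 normalized with the last visit low, S1 normalized with the last visit high, and E escaped. At each visit, with that visit's p:

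N′ = pN; S0′ = q(N + S0 + S1); S1′ = pS0; E′ = E + pS1

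The confirmed rule inserts a state M (one low visit so far): N′ = p(N + M); M′ = qN; S0′ = q(M + S0 + S1); the rest is unchanged.

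**Chance of being scored as escaped, ranges over CV 20–50%.**

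| True UFC (x ULN) | 4 visits, as written | 4 visits, confirmed | 12 visits, as written | 12 visits, confirmed |
|---|---|---|---|---|
| 0.9 | 5–13% | 2–4% | 29–55% | 26–46% |
| 1.0 | 22–24% | 6% | 77–82% | 59–62% |
| 1.1 | 27–30% | 3–6% | 89–92% | 34–59% |
| 1.2 | 11–29% | 0–5% | 60–92% | 7–48% |
| 1.3 | 3–27% | 0–3% | 24–90% | 1–34% |
| 1.5 | 0–16% | 0–1% | 2–73% | 0–13% |

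**Step 4. Timing.** After a chance normal core visit, the next two core visits are both high with probability p². At 1.1 x ULN this is 0.577² = 33% to 0.780² = 61%. Such an escape is timed at one visit interval, 4 weeks at this stage, so false escapes cluster early.

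**Step 5. Dose condition.** For a patient below 30 mg bid with no AE-led reduction or discontinuation, the probability is 0.

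**The case against.** Several points on the other side have force.

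- **The dose condition is a real filter.** A patient who loses control below the ceiling has escalation resumed (Protocol 5.5.4), so is not held at a fixed dose. In the preliminary data 1 + 3 + 3 + 1 + 2 = 10 of 11 patients had a normal UFC at 20 mg bid or less and one at 50 mg bid. The documents do not show how many patients sit near ULN at their highest tolerated dose, so the number of false escapes in this trial cannot be stated.
- **Entry is not a single urine.** It is a visit mean of two or three. The calculation already allows for that.
- **The plan is consistent with itself.** Mean UFC at or below ULN is its definition of controlled at every visit. A patient admitted by chance is uncontrolled only in the underlying mean.
- **The stakes are modest.** Escape is a descriptive secondary analysis without a test. Control rates by visit and listings of all laboratory values are also planned.

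Three stronger readings are tempting and are not supported. A reader might infer that every such patient is scored as escaped; it is a probability, and a small one in the core phase once true UFC is well above ULN. A reader might count all eight core visits from Week 2, which at CV 30–50% gives 73–76% at 1.1 x ULN. That needs the highest tolerated dose from Week 2, whereas new patients start at 2 or 5 mg bid and step up on Days 21, 35, 49 and 63. If the ladder is 2-5-10-20-30 (inferred, as the design figure is not available), 30 mg bid is reached on Day 63 or Day 49, leaving four or five core visits. Five visits give 40–44% at 1.1 and 4–40% at 1.3 x ULN. Eight could fit only patients at their highest tolerated dose almost from the start, such as some re-entrants. Finally, a reader might take the protocol's statement "Four patients experienced AEs consistent with cortisol withdrawal and they all improved upon dose reduction" to mean that 4 of 11 were exposed. Those events point to a marked fall in cortisol, not to incomplete response near ULN. They also arose in the core PoC cohort, which this SAP's analyses do not cover unless the patients re-entered.

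**Conclusion.** The point stands in limited form. Entry and exit share one threshold, only the exit is confirmed, and the stated reason for confirmation applies to both. A stable patient slightly above ULN at the highest tolerated dose can be scored as escaped without any loss of effect. The risk is moderate in the core phase (at most 30% over four visits) and can be large over the extension, where visits accumulate and rest on two urines.

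The sizes depend on an assumed CV, independent visits, constant true UFC and the highest tolerated dose from Day 70; correlation between visits would change them. They are conditional on such a patient existing and are not estimates of inflation in this trial. Confirmation reduces the artefact but does not remove it: at 1.0 x ULN over 12 visits it falls only from 77–82% to 59–62%, because the shared threshold remains. That supports an added analysis, not replacement of the protocol's definition.

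**What to change.** Keep the Protocol 9.5.2 definition as the main escape analysis, so that protocol, SAP and earlier reports stay aligned. Before the final lock, add to SAP 7.3.2.4 a pre-specified second analysis in which normalization means mUFC at or below ULN on two consecutive scheduled visits. Start time to escape at the second, confirming visit: starting at the first would build in event-free time, since no escape can occur before the confirming visit. Leave the escape rule and the dose condition unchanged. Report both analyses per cohort, and state how many escapes in the main analysis follow only a single normal visit.

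The cost is a paragraph of SAP text and one further run on existing data. The downside is that patients with only one normal visit drop out of the second analysis, so a genuine loss of control straight after one normal visit shows only in the main one.

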5.5.4 Permitted dose adjustments and interruptions of study treatment

LCI699 dose will be titrated as outlined in [Section 3.1](#) or until normalization of UFC (below upper limit of normal, as per local lab levels). For patients who are unable to tolerate the protocol-specified dose scheme, dose adjustments are permitted. The following guidelines should be followed:

- If the patient has not reached normalization of UFC, but does not tolerate the current dose, administration of an intermediate dose between the current (untolerated) and preceding (tolerated) dose or repeated administration of the preceding, tolerated dose should be considered.
- If the patient has reached normalization of their UFC, but the current dose is no longer tolerated, an intermediate dose between the current dose and previous dose should be considered.
- If the patient had reached normalization of their UFC, but the current dose is no longer efficacious based on on-going UFC measurements, dose escalation should resume.
- If the patient has low serum cortisol or $UFC < LLN$, and the patient has signs/symptoms of adrenal insufficiency, a dose reduction of LCI699 should be considered.

These changes must be recorded on the Dosage Administration Record eCRF.

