## Document history

---

Version	Date	Changes
Final 1.0	16-Oct-2013	NA
Amendment 2	13-Mar-2019	Updated for the Final CSR analysis The main changes are: Section 1: Addition of further protocol amendment details Section 3: Update of study objectives to align them with the Final CSR Section 5: Update to cutoff date used for Final CSR analyses Section 7.3.2: Secondary efficacy analyses updated Section 7.4: PK evaluations removed for Final CSR Section 7.5.1.3: Addition of text for the AE disclosure outputs Section 7.5.1.4: Removed specific AE summaries to be performed Table 8-2: Addition of extension 2 visits to the visit summary table.

---

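### Protocol 9.5.2 and SAP 7.3.2.4 set the highest tolerated dose by different rules, so the same patient can be an escape under one and censored under the other; both also censor withdrawal for lost control below 30 mg bid

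*SAP*

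**What the plan says.** Both documents define escape as loss of UFC control at two or more consecutive visits on the HTD, after earlier normalisation. Both date it at the first of those visits, and both censor everyone else at the last visit with a mean UFC. The HTD therefore decides who has an event. Three rules for setting it matter here.

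- **Stopping for an AE.** Protocol 9.5.2: "For patients who discontinue the study due to AEs, the dosage at discontinuation will be considered the highest tolerated dose". SAP 7.3.2.4: "For patients who discontinue the study due to AE, the highest tolerated dose is the highest prior dose at which no intolerable AE was reported".
- **Dose reduction.** Protocol 9.5.2: "For patients who have dose reduction due to safety reasons, the resulting reduced dose will be the highest tolerated dose". In the SAP the trigger is an intolerable adverse event, and "the highest tolerated dose is the highest dose at which no AE requiring dose reduction is reported".
- **Neither of these.** With no safety issue the HTD is 30 mg bid in both documents. In all other situations both say the HTD was not reached, so no escape can be recorded.

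The rationale for Amendment 5 in the Protocol states the intent as "The highest tolerated dose is the highest dose without a drug-suspected adverse event (AE), up to the maximum LCI699 dose of 30mg bid". The SAP document history, for the version of 13 March 2019, records "Section 7.3.2: Secondary efficacy analyses updated" and does not mention a departure from Protocol 9.5.2.

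Protocol 3.5 and 5.5.7 foresee withdrawal of patients who do not respond adequately.

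**The concern.** Escape is a secondary objective that SAP 3.2 keeps in the Final CSR, reported as a Kaplan-Meier median and curve for each cohort. Two operative sections give different rules for the dose on which the event depends. Two analysts following the two documents could classify the same patient differently, and the reader of the report would not know which rule had produced the curve.

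The second issue is common to both texts. Kaplan-Meier assumes that a censored patient has the same future risk of escape as those still followed. A patient withdrawn because control was lost does not, so censoring that patient makes control look more durable than it was.

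**Working it through.** The escape analysis has no planned figure to reproduce. The check applies each document's HTD rule to assumed histories, using the event and censoring rules that they share. Doses are in mg bid. Time is counted in weeks from the first normal visit. The histories are illustrations, not patients in the documents.

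| History | Protocol 9.5.2 | SAP 7.3.2.4 |
|---|---|---|
| 1. Normal at week 4; one uncontrolled visit on 20; uncontrolled on 30 at weeks 10 and 14; AE stop on 30 | HTD 30: escape at 10 − 4 = 6 | HTD 20: censored at 14 − 4 = 10 |
| 2. Normal at week 4 on 10; uncontrolled on 10 at weeks 6 and 8; raised to 20, one visit at week 10; AE stop on 20 | HTD 20: censored at 10 − 4 = 6 | HTD 10: escape at 6 − 4 = 2 |
| 3. Only ever on 5; normal at week 2; uncontrolled at weeks 4 and 6; AE stop | HTD 5: escape at 4 − 2 = 2 | No prior dose: HTD undefined |
| 4. Reduced from 20 to 10 for an intolerable AE, then re-escalated to a tolerated 15 | HTD 10 | HTD 15 |
| 5. Normal on 10 at week 4; uncontrolled on 20 at weeks 10 and 14; no AE; withdrawn for unsatisfactory response | HTD not reached: censored at 14 − 4 = 10 | Same: censored at 10 |
| 6. As 5, but the uncontrolled visits are on 30 | Escape at 10 − 4 = 6 | Same: escape at 6 |

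**Histories 1 to 3** show the AE-discontinuation conflict. It can move a patient in either direction, and the SAP rule has no answer when only one dose level was taken. History 2 needs two uncontrolled visits before the dose is raised. Protocol 5.5.4 makes that less likely: if a patient had normalised but "the current dose is no longer efficacious based on on-going UFC measurements, dose escalation should resume". History 1 does not depend on this, because 30 mg bid is the maximum.

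**History 4** shows that the dose-reduction rules can also give different doses. They agree when the patient goes back to, and stays on, the highest dose already tolerated. They also agree when the patient is reduced to a tolerated intermediate dose, as Protocol 5.5.4 allows where "an intermediate dose between the current dose and previous dose should be considered".

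**Histories 5 and 6** differ only in the dose on which control was lost. One patient is censored and the other is an event, under both documents.

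**Size of one reclassification.** An event lowers the Kaplan-Meier estimate S by S/n, where n is the number at risk. With no earlier escape S = 1, so the drop is 1/n:

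- n = 15 (planned expansion cohort, SAP section 6, all at risk): 1/15 = 6.7 points.
- n = 4 (follow-up cohort, assuming the 19 enrolled under Amendment 4 less the planned 15): 1/4 = 25.0 points.
- n = 10 (late follow-up, for illustration): 1/10 = 10.0 points.

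The step grows as patients leave. The Amendment 9 rationale has 10 of 19 ongoing on 3 May 2018, and the Final CSR cutoff falls when the last patient completes or discontinues, so no firm upper limit can be set. If nobody is affected, the effect is zero.

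**The case against.** The case on the other side has five parts.

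1. **No affected patient is documented.** The Amendment 5 section of the Protocol reports one AE withdrawal under Amendment 4. It does not say whether that patient had normalised or had two uncontrolled visits at the relevant dose. This stands, and the effect is stated only as an illustration.
2. **The SAP wording may be deliberate.** It is closer than Protocol 9.5.2 to the intent given for Amendment 5. This also stands. It does not remove the need to declare a departure from a rule that the current Protocol still carries.
3. **Withdrawal below 30 mg bid should be uncommon.** Protocol 5.5.4 says escalation should resume when control is lost, and history 5 departs from that. This limits how often the second issue arises but does not rule it out, because Protocol 3.5 and 5.5.7 provide for withdrawal without requiring that 30 mg bid be reached first.
4. **The HTD condition is part of the objective.** Censoring below it follows from the definition, and on this issue the two documents do not contradict each other. That is right, and it is why a sensitivity analysis is proposed instead of a new main analysis.
5. **The withdrawals remain visible elsewhere.** Disposition reasons (SAP 7.1.2) and responder rates (SAP 7.3.2.1) show them. This is partly true: a patient withdrawn for this reason in an extension counts as a non-responder at later visits. The escape curve still treats that patient as uninformatively censored.

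A reader might also infer that the SAP definition was changed in 2019, with open-label data in hand, to reduce the number of escapes. The documents do not support this. The history lists only main changes, has no entry for a first SAP amendment, and does not show when the wording diverged. The change can also add escapes, as history 2 shows.

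**Conclusion.** The two documents give incompatible HTD rules for patients who stop for an AE, and nothing else in them settles which rule governs the analysis. The dose-reduction rules differ as well. Separately, both documents censor withdrawal for lost control below 30 mg bid without a dose-limiting AE, which biases the curve towards durability when it occurs.

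The consequence is confined to a descriptive secondary analysis, but in cohorts this small one patient is visible: 6.7 points with 15 at risk and 25 points with 4. Those figures assume that everyone in the cohort normalised and is still at risk, that no escape came earlier, and, for the second, that the follow-up cohort has 4 patients. The number affected by either issue is unknown and may be zero.

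It would go too far to conclude that the reported escape results are wrong, that requiring the HTD is a mistake, or that the SAP rule always favours the drug. The documents establish none of these. The plan should be corrected before the Final CSR analysis.

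**What to change.** 1. Reconcile Protocol 9.5.2 and SAP 7.3.2.4 so that one HTD definition applies for analysis, or state and justify the departure in the SAP. It should cover AE discontinuation, including patients who took only one dose level, and dose reduction, including later re-escalation.
2. List every patient whose escape status or date differs between the two wordings. If there are none, the listing shows it.
3. Keep the HTD-based analysis as the main one. Add one sensitivity Kaplan-Meier analysis that counts withdrawal for unsatisfactory response after loss of control as an event, and report how many patients it affects.
4. Fix the dating of that event in advance, in line with the plan's own convention: the first of the consecutive uncontrolled visits on the final dose or, if there is only one such visit, that visit. History 5 would then be an event at 10 − 4 = 6 weeks instead of censored at 10.

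The cost is a wording change, one listing and one extra curve from data already collected. The durability estimate may look slightly less favourable. This concerns the analysis definition only; no dose or clinical rule is proposed.
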